6.6.3 Clinical Malaria during Follow-up

Participants who have an episode of confirmed clinical malaria at any time after enrolment up to the last follow-up visit and for one month afterwards will have blood taken for parasite genetic analysis.

6.7. Blood volumes

The blood volumes for the protocol mandated tests are as follows:

1. PCR: 1ml
2. Dried blood spots for lumefantrine level: 0.2ml
3. Dried blood spots for genetics: 0.4ml
4. Storage for serology at baseline 2ml

Maximum blood volumes are presented below for adults for the maximum of three periods (84 days) of follow up. The maximum blood volume is the total amount taken if the participants returns

for follow-up on 3 consecutive occasions and had all blood samples taken. The maximum blood volume will be approximately 10.4 ml (less than 10% of total blood volume taken over 8 weeks as recommended by WHO- *Bulletin of the World Health Organization* 2011;89:46-53).

Allowing for the possibility that we may need to repeat blood tests, we may add 10.4 ml to these estimated maximum blood volumes.

Blood samples collected from this study will be stored no longer than 10 years using codes assigned by the study team or their designee(s). Access to research samples will be limited using either a locked room or a locked freezer.

6.8. Analysis of blood samples

6.8.1 Parasite PCR

This is required for the primary study objective. Blood samples will be analysed in the Molecular Tropical Medicine Laboratory, Bangkok, Thailand using PCR to identify which individuals have malaria parasites of any species. It is anticipated that results will be available around 3 to 6 months after collecting each sample, thus they will not be used to guide antimalarial treatment at the time of testing. The study teams will be informed which samples were positive for malaria and they will follow-up positive participants to conduct a brief clinical assessment. Any individuals who are symptomatic will be referred to the village malaria worker or clinic for testing and treatment.

6.8.2 Parasite genetic analysis

Blood samples (dried blood spots) for parasite genetic analysis will be obtained and stored from all subjects recruited with subject's consent. In individuals in whom parasites are found by PCR, samples will be processed for parasite genetic analysis. Genetic samples (in the form of dried blood spots or extracted DNA) will be stored (for a maximum of 10 years) at the Molecular Tropical Medicine Laboratory, Bangkok, Thailand. In those with confirmed clinical malaria, parasite genotyping will be performed at the Wellcome Trust Sanger Institute in Hinxton, UK or other suitable laboratory using a set of informative single nucleotide polymorphisms selected from whole genome sequencing. The subject will be asked for consent for this transfer during the initial informed consent process. A material transfer agreement will be in place if required before any samples are shipped. The results of the parasite genotyping will not be reported back to the subjects. This analysis will only be done for those with confirmed clinical malaria as it is anticipated that there will be insufficient genetic material in samples taken from those with asymptomatic infection due to the low parasite burden in these individuals.

6.8.3 Lumefantrine level

Blood samples (dried blood spots) for lumefantrine level will be taken at each follow-up visit. These will be analysed in the Pharmacology Laboratory at MORU in Bangkok, Thailand.

6.8.4 Serology

Among those who specify by written consent, the serology samples will be analysed for diagnostic markers of other infectious diseases.

6.9 Study drug

6.9.1 Artemether-lumefantrine

Currently available as standard tablets containing 20 mg artemether and 120 mg of lumefantrine, in a fixed-dose combination formulation. It is included in this formulation on the WHO Model List of Essential Medicines [21].

Target dose/range:

The dose of artemether-lumefantrine is administered as a twice daily dose for 3 days for a total of 6 doses (an initial dose, second dose after 8 hours and then twice daily – morning and evening – for the following two days) followed by twice daily once a week according to the treatment schedule in Appendix 2.

6.9.2 Multivitamin

The multivitamin will be multivitamin (HEXA CMP, Chemephand Medical Co., Ltd.) or suitable equivalent alternative administered as a once daily dose using the treatment schedule in Appendix 2. This multivitamin does not contain any compound with antimalarial activity. Its components are: Vitamin-A: 5000 USP units, Vitamin D: 400 USP Units, Ascorbic acid: 75 mg, Thiamine Mononitrate: 2 mg, Riboflavin: 3 mg and Niacin amide: 20 mg.

6.10 Epidemiological data on place of residence, work, travel history and malaria risk

In order to have a greater understanding of the possible sites of malaria transmission, and to relate genetic diversity to geographical location, participants will be asked a short set of questions on their place of residence, place of work and their history of travel plus possible risk factors for malaria. This is to obtain a detailed understanding of the behaviours and risk factors for malaria infection. We will collect GPS coordinates of the places of residence of all participants. In a subset of participants, GPS coordinates will be collected for their travel patterns during follow-up including place of work, forests, forest camps, farms or plantations to identify places where their infection may have occurred. The size of this subset will be determined by the availability of GPS devices with the number being limited to 50 participants at any one time. The GPS devices will be offered to unselected trial participants whenever they are available. We will collect all available local malaria treatment records to describe how the study population compares to the overall population who receive treatment for malaria and this will allow us to better understand local malaria epidemiology and transmission patterns. All personal information will be anonymised so that no individual can be identified from their treatment records, through interviews, or from mapping data.

6.11 Malaria incidence data

Passive surveillance data from all available sources for the study province collected by the Cambodia National Center for Parasitology Entomology and Malaria Control will be analysed to identify any changes in malaria incidence rate in study villages before, during and after the study where PA prophylaxis was administered compared to non-study villages.

Enrolled participants who experience an episode of confirmed clinical malaria during follow-up will be linked back to their individual case records to quantify the incidence of clinical malaria in each study arm.

6.12 Analysis

6.12.1 PCR for parasites

PCR will be used to identify which individuals have parasites at enrolment (prior to taking the study medicine) and at each follow-up visit and is required for the primary study objective.

6.12.2 Parasite genetics

Parasite DNA will be used for genomic studies including but not limited to parasite species confirmation, microsatellite typing to identify parasite clones and single nucleotide polymorphisms (SNP) typing/whole genome sequencing to generate data for studies of the geographic origins of the parasites.

6.12.3 Lumefantrine levels

Lumefantrine levels will be used to confirm which patients had taken lumefantrine and to measure the amount present in the blood.

6.12.4 Serology

The serology sample will be used for anonymized investigation of the prevalence, incidence, association with fever, and risk factors for other common infectious diseases affecting the study population. Samples will be stored for later analysis.

6.13 Discontinuation/ Withdrawal of Participants from the Study

Each participant has the right to discontinue the study drug or the study at any time. Data accrued up until the time of discontinuation will be used in the analysis.

In general, the investigators will be required to make every effort to perform the study procedures until completion of follow-up (maximum 3 visits over 84 days), including in the following situations:

- Significant non-compliance with treatment regimen or study requirements
- An adverse event which requires discontinuation of the study medication or results in inability to continue to comply with study procedures
- Disease which requires discontinuation of the study medication or results in inability to continue to comply with study procedures
- Loss to follow up (every attempt should be made to re-contact the participant)

However, the investigator may discontinue participation in the study of a participant if he or she considers it necessary.

In addition, the participants always have the right to withdraw consent in writing or verbally.

The reason for withdrawal or discontinuation, if available, will be recorded in the CRF. If the study drug or participation in the study is discontinued due to an adverse event, the investigator will arrange for follow-up visits at least until the adverse event has resolved or stabilised.

If a participant does become pregnant during participation in the study, they will be withdrawn from the study immediately upon it being reported to the study team. Any pregnancy must be reported to the Principal Investigator within one working day of awareness. The PI must take all reasonable efforts to discover the outcome of the pregnancy and fill out the pregnancy form. If there is a congenital abnormality or a still born baby, this needs to be reported as a serious adverse event.

6.14 Source Data

Source documents are original documents, data, and records from which participants' CRF data are obtained. These include, but are not limited to, village malaria and clinic records (from which medical history and previous and concurrent medication may be summarised into the CRF), clinical and office charts, laboratory and pharmacy records, diaries, microfiches, radiographs, and CRFs.

CRF entries will be considered source data if the CRF is the site of the original recording (e.g., there is no other written or electronic record of data). In this study, the CRF will be used as the source document for most of the data points.

All documents will be stored safely in confidential conditions. On all study-specific documents, other than the signed consent form, the participant will be referred to by the participant number and initials, not by name.

7. STUDY DRUGS

7.1 Storage of Study Drugs

All efforts will be made to store the study drugs in accordance with the manufacturers' recommendations in a secure area. This may be difficult at some sites where air-conditioned storage rooms are not available. The ACT should be stored between 15°C to 30°C (59°F to 86°F).

Where this is not possible and monitored storage conditions do not meet the recommendations, the artemisinin-derivatives and partner drug content of batches of ACT will be retested at the end of the study.

7.2 Compliance with Study Drugs

Study drugs will be administered as Directly-Observed-Therapy (DOT) on the first day. Where possible, study drugs will also be administered as DOT on days 2 and 3. Where DOTs is not possible, the participant will be contacted by the study team by telephone or in person to ensure they take the second and third doses of medication and to ensure they follow the correct procedure in case of vomiting. If the participant vomits, and is re-dosed; this will be recorded in the CRF. If

vomiting within 1 hour occurs again after retreatment, no repeat dosing is allowed. All drug doses will be recorded in the CRF. To maximise adherence to the study medication, the study will be preceded by a period of community sensitisation and engagement including information sessions on the importance of taking all three doses of medication. The participants will be requested to take each dose with food to maximize absorption of the lumefantrine.

7.3 Accountability of the Study Treatment

All movements of study medication will be recorded. Both study medication of individual participant and overall drug accountability records will be kept up to date by the study staff.

7.4 Concomitant Medication

Throughout the study, investigators may prescribe concomitant medications or treatments deemed necessary (e.g. antipyretics or anti-emetics) to provide adequate supportive care except for antibiotics with antimalarial activity unless unavoidable (e.g. doxycycline, azithromycin). If these are required the participants will be kept in the study and this will be noted as a protocol deviation. Anti-emetics should not be prescribed as a prophylaxis if no nausea or vomiting is present.

Antimalarials for symptomatic, confirmed malaria infections will be prescribed as described above. Any medication, other than the study medication taken during the study will be recorded in the CRF.

8. SAFETY REPORTING

This trial will use drugs that have either been registered or evaluated extensively. To add to the evidence base for safety of AL as prophylaxis, we will record and review all Adverse Events (AEs) and Serious Adverse Events (SAEs) that are reported to occur in the study.

A symptom questionnaire will be performed on enrolment and at each subsequent follow-up visit to the health care center, to aid in the identification of adverse events. In addition, enrolled individuals will be encouraged to promptly report any unexpected symptoms or illnesses between follow-up visits to the study team.

The investigator is responsible for the detection and documentation of events meeting the criteria and definition of an adverse event (AE) or serious adverse event (SAE), as provided in this protocol.

All SAEs and AEs will be promptly documented from the moment of drug administration in the study to discontinuation of the participant from study participation. Any events occurring between screening and drug administration will be considered as baseline, preexisting conditions.

All adverse events must be recorded in the AE/SAE CRF. To avoid colloquial expressions, the adverse event should be reported in standard medical terminology. Whenever possible, the adverse event should be evaluated and reported as a diagnosis rather than as individual signs or symptoms. If a definitive diagnosis is not possible, the individual symptoms and signs should be recorded. Whenever possible, the aetiology of the abnormal findings will be documented on the CRF. Any additional relevant laboratory results obtained by the Investigator during the course of this study will be recorded on the CRF.

If the event meets the criteria for “serious”, the SAE must be reported to the PAL-Cambodia safety team within 24 hours from the time that the event was identified. If further data is required, additional documentation can be submitted. All SAEs must be followed until resolution, or until the SAE is deemed permanent or leads to death.

Samples will be shipped for PCR to a molecular laboratory where they will be analysed in batches. Following quality control results will be available approximately 3-6 months from the time of collection. The list of positive tests will be returned to the field sites. If a participant is found to have a plasmodium infection, and has not already received antimalarial treatment subsequent to the sample being collected, then these individuals will be contacted by a local health worker, and if a participant reports fever or illness they will be offered appropriate diagnosis and treatment.

8.1 Definitions

8.1.1. Adverse Event (AE)

An AE is any undesirable event or clinical deterioration that occurs to a study participant during the course of the study; that is, from the time of administration of study drugs until study ends (i.e., until the follow up visit) whether or not that event is considered related to the study drugs, or to a concomitant drug or procedure: e.g.

- any unfavourable and unintended symptom
- physical sign
- abnormal laboratory result
- an illness

Any new clinical sign or clinical deterioration that occurs between signing the consent form and the administration of study drugs is not an AE. This information will be recorded in the medical records, as a pre-existing condition.

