5.4.2. Secondary Endpoints

1. 28-day, 56-day and 84-day PCR *Plasmodium* positivity rate for each *Plasmodium* species

2. Proportion of participants with confirmed malaria reported between day 0 and day 28 for each species
3. Description of epidemiological situation of malaria in the study areas from passive surveillance data.
4. Prevalence of *Kelch13* mutations and other genetic markers of antimalarial drug resistance of known functional significance.
5. Incidence of adverse events and serious adverse events by study arms during the course of prophylaxis.
6. Data on the place of residence, work, recent travel history and mobile phone use.
7. Detailed data and GPS mapping on a subset of participants and their peers relating to the behaviours and risk factors associated with malaria infection.
8. Overall prevalence of Plasmodium at baseline, stratified by season and risk factors.
9. Day 0, 28, 56 and 84 capillary blood levels of lumefantrine.
10. Prevalence of serological diagnostic markers of other infectious diseases.

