6.5. Study drug administration

Overview PAL drug regimens	
ACT arm	Multivitamin arm
Artemether -lumefantrine x 3 days followed by 1 day per week	Multivitamin x 3 days followed by 1 day per week

Participants will be treated with weight-based doses according to the schedule in Appendix 2.

The study drugs will be administered by trained study staff.

If the participant vomits within half an hour after intake of the antimalarial drugs, the dose will be repeated. If vomiting occurs between half and one hour, half of the dose will be repeated. If vomiting occurs more than one hour after drug administration, no repeat dosing will be done. Repeat doses will be recorded on the CRF. If vomiting within 1 hour occurs more than one time, no repeat dosing is allowed. The participant will then be treated at the discretion of the investigator.

The prophylaxis will start with a 3-day course of twice daily AL. This will be followed by 2 doses 8 hours apart on one day per week during the time that the person is travelling in the forest and for 4 weeks after leaving the forest.

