6.6. Follow-up

Participants will be asked to return for a follow-up assessment any time from 28 to 35 days after commencing prophylaxis. This will be regardless of the duration of their visit to the forest or the number of times they visited it in that period. At this assessment, they will be interviewed about how long they spent in the forest, where they went, why, who they travelled with and about risk factors for infection. Brief physical examinations, vital sign and symptom questionnaire will be performed. They will also be asked to report any diagnostic tests and/or treatment for malaria during the preceding 28-35 days.

Blood sampling at follow-up

At each follow-up visit, the following blood will be taken:

All individuals:

- Parasite PCR (Up to 1 ml).

- Dried blood spot for lumefantrine level (0.2 ml)

In those with confirmed clinical malaria at any time point between enrolment and follow-up:

- Dry blood blots (0.4 ml, 3 spots) collected on filter papers for:
 - o Parasite DNA genotyping for genetic markers of antimalarial resistance.
 - o Parasite whole genome sequencing and barcoding to identify geographical origin of parasites and compare genotypes to identify persistent infections.

In individuals who are planning to return again to the forest within the following 28 days after the follow up visit, they will be asked to continue their weekly prophylaxis according to the original treatment allocation on enrolment. They will then be asked to return for a second follow-up visit a further 28 to 35 days later when the above procedure will be repeated. This will be repeated one more time. If the person cannot be followed up within the scheduled period, e.g. because they do not return from the forest in time, then they will be followed up at the first opportunity and this will be recorded in the CRF.

Thus individuals may take prophylaxis continuously for a maximum of 3 periods of 28-35 days in the forest plus 4 weeks after returning totaling 112 days. The choice of study medication for each individual will follow the initial assignment on enrolment throughout the follow-up period.

In those who do not declare an intention to return to the forest within 28 days at any follow-up visit, no further follow-up visits will be offered at that time but they will be asked to complete 4 weeks of prophylaxis following their last day in the forest as post-exposure prophylaxis.

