#### 4.4.5 Adverse events and serious adverse events by study arms during the course of prophylaxis.

Adverse events will be graded according to Common Terminology Criteria for Adverse Events (CTCAE) Version 5.0 November 2017.

All adverse event summaries will refer to treatment emergent adverse events, i.e. adverse events that newly started or increased in intensity after the study drug administration. AE summaries will be generated for all AEs that occurred after study drug administration, until the end of the study.

Incidence of adverse events and serious adverse events by study arms during the course of prophylaxis will be presented in the table 6a below. AE intensity and relationship to study drug wil be presented as in tables 6b and 6c. Graphical presentations might be considered when presenting these.

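### The adverse event window closes at the follow-up visit, but weekly study drug can continue for up to 28 days after it

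*Protocol*

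**What the plan says.** **AE window.** Protocol 8.1.1 defines an AE as an event occurring "from the time of administration of study drugs until study ends (i.e., until the follow up visit"). Section 8.1.2 defines an SAE as a kind of AE, so the same limit applies to it. Section 8 describes the documentation period differently: from drug administration until the participant discontinues participation, with no day given.

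**Dosing.** Under Protocol 6.5, weekly study drug continues "during the time that the person is travelling in the forest and for 4 weeks after leaving the forest". Section 6.6 says that for participants who do not intend to return to the forest, "no further follow-up visits will be offered at that time but they will be asked to complete 4 weeks of prophylaxis following their last day" there. It gives the longest continuous exposure as "a maximum of 3 periods of 28-35 days in the forest plus 4 weeks after returning totaling 112 days".

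**Visits.** Under section 6.6 the first visit falls "any time from 28 to 35 days after commencing prophylaxis" and the next "a further 28 to 35 days later", with at most three. Appendix 1 places them at D28-35, D56-63 and D84-91, and section 6.13 describes complete follow-up as three visits over 84 days. The symptom questionnaire is scheduled at day 0 and at these visits only.

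**Reporting.** Secondary endpoint 5 (Protocol 5.4.2) is "Incidence of adverse events and serious adverse events by study arms during the course of prophylaxis", and SAP 4.4.5 assigns the same quantity to Table 6a. Protocol 9.2.4 and SAP 4.4.5 also say that AE summaries run to the end of the study, which Protocol 8.1.1 equates with the follow-up visit.

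**The concern.** Section 6.6 expects some participants to take study drug after their last visit, and section 8.1.1 stops counting AEs at that visit. If 8.1.1 is applied, an event in the last weeks of dosing, including a hospitalisation, is neither an AE nor an SAE by definition. It would then be missing from an endpoint that is described as covering the course of prophylaxis.

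Section 8 states that AEs are recorded to add to the safety evidence for artemether-lumefantrine (AL) as prophylaxis. Extended weekly dosing is what distinguishes that use from treatment, and it is the later part of this dosing that falls outside the window. Sites could also classify the same late event differently, depending on whether they follow section 8 or section 8.1.1.

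**Working it through.** **Inputs.** Post-exposure dosing lasts 28 days after the last forest day (6.5, 6.6). Visit days come from 6.6 and Appendix 1. AL dose days come from Appendix 2: six starting doses, then two doses on each of days 7, 14, 21 and so on, counting enrolment as day 0. Planning minimum of 10 days at risk per episode (9.1). Departure up to 72 hours after enrolment (5.5.2).

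**The plan's own maximum.** Three periods plus four weeks: 3 × 28 + 28 = 112 days, as stated. With 35-day periods it is 3 × 35 + 28 = 133, which does not match. Against follow-up ending at day 84 (6.13), the gap is 112 − 84 = 28 days.

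**Formula.** End of dosing = last forest day + 28. Gap = max(0, end of dosing − last visit day). Uncovered share = gap / end of dosing.

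**Worst case: in the forest until the last visit**

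| Periods | 28-day visits | Latest Appendix 1 visit | Visits drifting by 35 days (6.6) |
|---|---|---|---|
| 1 | 28/56 = 50% | D35: 28/63 = 44% | D35: 28/63 = 44% |
| 2 | 28/84 = 33% | D63: 28/91 = 31% | D70: 28/98 = 29% |
| 3 | 28/112 = 25% | D91: 28/119 = 24% | D105: 28/133 = 21% |

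If 112 days is a hard cap, the three-period figures become (112 − 91)/112 = 19% and (112 − 105)/112 = 6%.

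**Same case by AL doses, 28-day visits, no dose on the final day.** The lower figure has the visit-day dose taken before the visit, the higher figure after it.

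- One period: 6/20 to 8/20 = 30% to 40%
- Two periods: 6/28 to 8/28 = 21% to 29%
- Three periods: 6/36 to 8/36 = 17% to 22%

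If a dose on the final day is also counted, the upper figures are 10/22 = 45%, 10/30 = 33% and 10/38 = 26%.

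**Shorter stays, one period**

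- 10 days from day 0: dosing to day 38. Day-28 visit 10/38 = 26%; day-35 visit 3/38 = 8%. By AL doses (16 in all): 2 to 4 uncovered (13% to 25%) after a day-28 visit, 0 to 2 (0% to 13%) after a day-35 visit.
- The same stay starting on day 3: dosing to day 41. Day-28 visit 13/41 = 32%; day-35 visit 6/41 = 15%.
- Forest exit by day 7 with a day-35 visit: gap 0.

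**Alternative visit timing.** Protocol 3.3 places the visit 28 ± 7 days after return from the forest, that is at exit + 21 to exit + 35. The gap is then at most 28 − 21 = 7 days.

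**Whether other text closes the gap**

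- Section 8 gives an undated end point, ties the investigator's duty to the protocol's own AE definition, and asks for self-report only between visits.
- Section 6.6.2 asks for symptom reports after enrolment without a stated end, but does not decide whether a reported symptom is an AE.
- Section 8.2 requires every SAE to be reported without an end date, but an SAE must first be an AE.
- Section 6.13 requires certain pregnancy outcomes to be reported as SAEs after withdrawal. This covers only those outcomes.
- Section 6.6.3 and Appendix 1 follow confirmed malaria for a month after the last visit, to D112. No equivalent exists for other events.

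**The case against.** The strongest counter-argument is that the course in endpoint 5 is never defined. Protocol 6.5 uses the word for the three-day start, and sections 3.3 and 6 place visits at the completion of a course. On that usage the AE window and the endpoint would agree. Section 6.6, however, calls the dosing after the last visit prophylaxis and counts it in the 112-day total. The narrower reading therefore leaves the conflict in place.

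A second argument is that section 8 is the operative instruction, and a participant still taking allocated drug is naturally still participating. That is a reasonable reading, but it is an inference and does not remove the stated limit in 8.1.1. Similarly, the end of the study in the SAP could bear its ordinary meaning, but the protocol's only gloss on it is the follow-up visit.

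Third, the large percentages need a stay in the forest up to the visit and depend on the visit timing in 6.6. This stands: the gap is 0 to 7 days under 3.3 and can be zero under 6.6.

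Fourth, one could simply relabel the endpoint as running to the last visit. That would be consistent and would avoid adding time without a scheduled questionnaire. It would also leave events on study drug unreported in a trial that sets out to describe the safety of this use.

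Finally, sections 6.5 and 7.2 say that staff administer study drug and that all doses are recorded. Section 7.2 provides directly observed dosing on the first day and, where possible, on days 2 and 3, so it does not establish staff contact during later weekly dosing.

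**Conclusion.** The concern holds. As written, the AE and SAE definitions can exclude 0 to 28 days of weekly dosing that endpoint 5 and SAP Table 6a are described as covering. The 28-day maximum follows from the protocol's own 84-day follow-up and 112-day exposure. The figures assume that the last forest day is not after the last visit; the shorter-stay figures assume one stay of the planning length.

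The consequence is limited. The endpoint is secondary, the rule is identical in both arms, and no between-arm bias is shown. Under the section 6.6 timing, the starting course and the weekly doses on days 7, 14 and 21 always fall inside the window. This is a contradiction that should be corrected; it does not threaten the primary comparison.

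**What to change.** - Reconcile Protocol 8 and 8.1.1 with endpoint 5, so that a single AE/SAE window runs from first dose to the end of each prophylaxis course. Define the end of participation and the end of the study to match; Protocol 9.2.4 and SAP 4.4.5 then follow.
- Extend the self-report request in section 8 to the end of dosing, in line with section 6.6.2.
- In SAP 4.4.5, state the window used and show events after the last visit separately by arm.
- Reconcile sections 3.3 and 6 with section 6.6 and Appendix 1 on visit timing, and the 112-day total with the 28-35 day periods and Appendix 1. The size of the gap depends on both; this point takes no position on which is right.

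The cost is protocol and SAP wording, some extra AE forms and one table split, with no new visit and no change to dosing. The drawback is that late events will be less completely ascertained without a questionnaire, and in an open-label trial spontaneous reporting could differ by arm. For that reason they should not be pooled unlabelled with events found at visits.
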